7 STATISTICAL METHODS

7.1 General Methodology

All summaries and statistical analyses will be performed using SAS, Version 9.4 or higher. Descriptive summaries will consist of frequencies and percentages for categorical measures and of the number of subjects [N], mean, standard deviation [SD], median, 25th and 75th quartiles,

minimum [min], and maximum [max] values for continuous measures. Descriptive summaries will be presented for each treatment group, BW strata, and all BW strata combined.

All statistical comparisons performed on the data will be done for exploratory analysis purposes only.

7.2 Adjustments for Covariates

Not applicable to this study.

7.3 Handling of Dropouts or Missing Data

It is not anticipated that there will be a need to adjust for missing data in this study. All data for this study will be analyzed as collected on the CRF.

The study will require a minimum of nine evaluable subjects within each BW strata and dose group. If less than nine subjects complete the minimum required study treatment duration (see Section 6.2.3) and have a post dosing assessment, then replacement subjects will be enrolled to replace the original randomized subjects who do not meet the minimum required study treatment durations. The treatment assignment for the replacement subject will be the same as the original subject who needed to be replaced. Data from the subjects who are replaced will be analyzed in the ITT and Safety analysis.

7.4 Interim Analyses and Data Monitoring

7.4.1 Formal Interim Analyses

No formal interim analyses of study data are planned to occur during the study.

7.4.2 DSMC Analyses

An independent DSMC will be used to review data generated in this study. A Charter for the DSMC outlining the membership, roles and responsibilities will be developed and finalized prior to the initiation of the study.

Available data on primary and secondary endpoints including adverse events will be included in each review. The DSMC can give recommendations of continuation of study, or temporary hold on study while additional data is further analyzed, or termination of the study. The DSMC will also review events that may constitute stopping criteria (see Protocol Section 7.1.1) on an as needed basis.

Unscheduled DSMC review of study data may occur at any time on an as-needed basis if requested by the DSMC.

The DSMC will review data for each dose/BW group to assess whether proceeding to lower BW and/or higher STP206 doses is warranted. Data reviewed at each

DSMC meeting will follow the following schedule:

- For the first group of subjects (Study Group 1a – BW 2000 to 1501 g and low dose STP206), data will be reviewed through the completion of dosing.
- For the next six DSMC reviews (Study Groups 1b through 4a), data the current dose group will be reviewed through the completion of dosing along with 30-day post dosing data from the prior dose group.
- For the final DSMC review (Study Group 4b), data through 30-days post dosing will be reviewed.

7.5 Multi-center Studies and Pooling of Centers

This study will be conducted in up to 20 centers. Data from all sites will be pooled. The pooled data will be summarized and analyzed.

7.6 Multiple Comparisons/Multiplicity

No adjustments for multiple comparisons or multiplicity will be made.

7.7 Use of an “Efficacy Subset” of Subjects

Not applicable to this study.

7.8 Active-Control Studies Intended to Show Equivalence

Not applicable to this study.

7.9 Examination of Subgroups

A subgroup analyses will be conducted for subjects whose gestational age at birth is ≤ 28 weeks, and > 28 weeks, respectively. Depending on the sample size, a subgroup analyses may be conducted for subjects whose gestational age at birth is ≤ 26 weeks, and 27 to 28, and ≥ 29 weeks.

8 STATISTICAL ANALYSIS

All statistical analyses will be performed using SAS® (version 9.4 or higher).

Unless otherwise noted, summary tables will only include data up to the Month 6 Post-Dose visit. Data collected after that will only be included in listings.

Safety and efficacy data will be summarized using BW strata. If deemed necessary, additional analyses may be conducted on pooled data across cohorts, where incidence of clinical events

(NEC, sepsis, feeding intolerance, death, morbidity/complications of prematurity) may be presented.

8.1 Disposition of Subjects

The number of subjects enrolled and the number of treated subjects will be summarized.

The number of subjects who completed the study, the number of treated subjects who discontinued from the study and the reasons for discontinuation from the study will also be summarized.

The Intent-to-treat (ITT) population will be used for this analysis.

The summary of subject disposition will be displayed by (i) dose group and BW stratum, (ii) by all BW strata combined for STP206 low dose, STP206 high dose and control group, and (iii) by investigation site and dose group.

8.2 Protocol Deviations

Protocol deviations will be recorded by the designated site CRA and provided by Leadiant for consolidation. Deviations will be coded by Leadiant as Critical, Major, or Minor. The tracker of deviations will be provided to [REDACTED] for integration in the analysis reporting.

8.3 Analysis Populations

8.3.1 Safety Population

The safety population will be all randomized subjects who received any amount of blinded study treatment. Subjects will be analyzed according to the treatment they actually received.

8.3.2 Intent-to-Treat (ITT) Population

The Intent-to-treat population will consist of all randomized subjects. Subjects will be analyzed according to the randomized treatment.

8.3.3 Per Protocol (PP) Population

The per-protocol population will consist of all randomized subjects who meet the Minimum Required Cumulative Dosing Days as indicated in Protocol Section 11.2.3, or have a clinical outcome of NEC (confirmed case), and do not have a critical or major protocol deviation. Subjects will be analyzed according to the treatment they actually received. This population may be used for analysis if subjects are dosed incorrectly.

Leadiant will review protocol deviations/violations to determine if a subject completed the study according to the protocol. This population of subjects will be identified at the time when all the data has been entered into the database and cleaned, prior to database lock.

The major protocol deviations may include:

- Deviations from inclusion criteria
- Deviations from exclusion criteria
- Use of prohibited concomitant medications (e.g., Products containing probiotic bacteria are prohibited)
- Subjects not meeting the minimum cumulative required duration of study treatment

The primary and selected secondary analyses will be repeated using the per-protocol population.

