6.4 Efficacy Variables

6.4.1 Primary Efficacy Variable(s)

No primary efficacy variable is defined for this study.

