6.4.2 Secondary Efficacy Variables

The secondary efficacy variables are:

- Incidence of suspected NEC (stage I)
- Incidence of confirmed NEC (stage II and higher)
- Incidence of Feeding intolerance
- Death
- Incidence of Sepsis
- Incidence of other neonatal complications of prematurity
 - ROP
 - IVH
 - BDP
 - Spontaneous Gastrointestinal Perforation
 - Patent ductus arteriosus requiring treatment with indomethacin, ibuprofen or surgery
- Number and percent of subject with STP206 organism (STP-6, STP-11) identified
- Time to first detection of STP206 organism (STP-6, STP-11)
- Number and percent of subjects that fall in the four growth classifications 1) appropriate for gestational age (AGA), 2) small for gestational age (SGA/Head-Spared), 3) SGA/Symmetric, and 4) large for gestational age (LGA). Where AGA is defined as both body weight (g) and head circumference (cm) are between 10th Percentile and 90th Percentile according to the gender specific growth Percentile charts. SGA/Head-Spared is defined as Body Weight (g) is <10th percentile, and Head circumference (cm) is between 10th Percentile and 90th Percentile according to the gender specific growth percentile charts. SGA/Head-Symmetric is defined as Both Body Weight (g) and Head circumference (cm) are <10th Percentile according to the gender specific growth percentile charts. LGA is defined as Both Body Weight (g) and Head circumference (cm) are >90th Percentile according to the growth percentile charts.

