8.6 Analysis of Efficacy Parameters

Descriptive summaries will consist of frequencies and percentages for categorical measures and of the number of subjects [N], mean, standard deviation [SD], median, 25th and 75th quartiles, minimum [min], and maximum [max] values for continuous measures. Descriptive summaries will be presented for each treatment group, BW strata, and all BW strata combined.

The incidence rates of the exploratory variables for those who received STP206 vs. control will be summarized and displayed.

The analyses of efficacy variables will be performed for ITT population only.

Efficacy will be displayed by (i) dose group and BW stratum and (ii) by all BW strata combined for STP206 low dose, STP206 high dose and control group.

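### SAP 8.3.3 makes per-protocol membership depend on confirmed NEC, contradicts its own deviation list so the direction of bias is unsettled, and announces PP repeats that SAP 8.6 rules out

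*SAP*

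**What the plan says.** **Who is in the PP set.** SAP 8.3.3 takes randomized infants who reach the minimum cumulative dosing days "or have a clinical outcome of NEC (confirmed case"), provided that no deviation rated critical or major applies. Its list of what may count as a major deviation then includes "Subjects not meeting the minimum cumulative required duration of study treatment".

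**What the set is for.** The same section says "This population may be used for analysis if subjects are dosed incorrectly", and later "The primary and selected secondary analyses will be repeated using the per-protocol population". It does not say which secondary analyses are selected.

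**What other sections say.**
- SAP 8.6: "The analyses of efficacy variables will be performed for ITT population only".
- SAP 6.4.1: "No primary efficacy variable is defined for this study". The primary endpoint (Protocol 6.3.1) is safety, and SAP 8.7 assigns safety to the Safety population.
- SAP 6.4.2 lists "Incidence of confirmed NEC (stage II and higher") as a secondary efficacy variable.
- SAP 11 lists NEC tables 14.2.2.1 to 14.2.2.8, all on ITT. The only PP tables listed are infant baseline characteristics, but tables may be added after the SAP is final.
- Protocol 10.8.2 stops study drug at once when NEC is diagnosed.

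**The concern.** A per-protocol set should be defined by adherence, not by the result. Here two infants with the same short exposure are treated differently: the one with confirmed NEC has a route in, and the one who stopped for sepsis, feeding intolerance or death without NEC has none. Such stops are foreseeable. Protocol 9.5.1 and 10.8.2 withdraw infants after prolonged loss of enteral intake or prolonged dose suspension, and with a live oral product these stops could be related to treatment.

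The second problem is that the section undoes its own rule. Because diagnosed NEC ends dosing, many NEC cases may fall short of the minimum. The entry clause admits them and the deviation bullet can remove them. Whoever derives the set must choose, and the choice moves the PP NEC rate in opposite directions.

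Preliminary NEC efficacy is a stated purpose of the study (Protocol 6.1). Whether a PP NEC result appears at all is also unsettled, since 8.3.3 and 8.6 disagree.

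**Working it through.** The plan states no PP NEC rate, power or effect size, so there is no figure to reproduce. What follows is algebra on the two readings.

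**Inputs**
- p, true NEC rate: 10% in both arms. This is the background figure for VLBW infants in Protocol 5.1, used here as an assumption; the 2000 to 1501 g stratum lies outside VLBW.
- s, share of non-NEC infants who are short-dosed: not in the documents, so varied. One anchor is SAP 7.3, which requires nine evaluable infants per group of about 12, so 3/12 = 25% may be non-evaluable before replacement.
- q, share of NEC cases who are short-dosed: not in the documents, so varied.

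**Reading A: the NEC clause operates.** All cases stay and short-dosed non-cases leave:

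PP rate = p / [p + (1 − p)(1 − s)]

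| s | p = 10% | p = 5% | p = 15% |
|---|---|---|---|
| 10% | 0.10/(0.10 + 0.81) = 11.0% | 5.5% | 16.4% |
| 20% | 0.10/(0.10 + 0.72) = 12.2% | 6.2% | 18.1% |
| 30% | 0.10/(0.10 + 0.63) = 13.7% | 7.0% | 20.1% |

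The rate is overstated for any s above zero.

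**Arm difference on reading A, with no true effect (p = 10%)**
- s equal in both arms, for example 25% and 25%: 12.9% v 12.9%, no difference.
- s = 30% on STP206 and 10% on control (assumption): 13.7% v 11.0%, a difference of 2.7 points and a ratio of 0.91/0.73 = 1.25.
- s = 25% v 0: 12.9% v 10.0%, +2.9 points. Reversed: −2.9 points, an apparent benefit.

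Eight groups of 12 at 2:1 give 64 v 32 infants. In 20,000 simulated trials of that size, the 25% v 0 imbalance gave a standard deviation of the difference of about 7 points. A two-sided 5% Fisher test rejected in 4.1% of runs (5.1% with the imbalance reversed), against 3.3% with no short dosing.

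**Reading B: the deviation bullet operates.** Short-dosed infants leave whether or not they had NEC:

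PP rate = p(1 − q) / [p(1 − q) + (1 − p)(1 − s)]

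With p = 10% and s = 25%, the non-case term is 0.90 × 0.75 = 0.675:
- q = 50%: 0.050/0.725 = 6.9%
- q = 75%: 0.025/0.700 = 3.6%
- q = 100%: 0%

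The rate falls below p whenever q exceeds s, which is to be expected when NEC itself ends dosing.

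**Reporting.** Both halves of the PP repeat sentence collide with other text. The only primary analysis is safety, which 8.7 places in the Safety population. Secondary efficacy is placed in ITT alone by 8.6.

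**Who counts as short-dosed.** The minimum days are identical in Protocol Table 2 and SAP 6.2.3 and equal 70.0% to 71.4% of intended days (49/70 = 70.0%, 45/63 = 71.4%). The protocol footnote says 70% and the SAP footnote 75%; 75% of 77 days is 57.75, so 58 days rather than the tabled 54. SAP 8.3.3 also points to Protocol 11.2.3 for these minimums, but that section covers IVH; dosing duration is in 11.3.2.

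**The case against.** The strongest reply is that little depends on this set. SAP 7.1 makes every comparison exploratory, the sample size has no statistical basis, and 8.6 summarizes efficacy on ITT. PP use is worded as optional, NEC is not named for repetition, and every listed NEC table is ITT. Membership is settled before database lock, and Protocol 9.1 does not expect many non-evaluable infants.

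Most of this stands, and it limits the harm. It does not remove the contradictions. Besides the optional sentence, 8.3.3 has one that says analyses will be repeated, the selected analyses are never named, and SAP 11 leaves room for new tables. Fixing membership before lock does not fix which analyses are chosen.

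A reader might go further and infer that the plan commits to a PP NEC analysis that overstates NEC and creates a false arm difference. The documents do not support that. The deviation bullet can reverse the direction. A PP NEC analysis is possible but not specified. On reading A an arm difference needs unequal non-NEC short dosing, for which the documents give no rates, and at moderate imbalance it is small beside chance variation.

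**Conclusion.** The point holds as a defect of definition and consistency. PP membership depends on the outcome, the section contradicts itself on short-dosed NEC cases, and its repeat sentence conflicts with 8.6, 8.7 and the table list. At an assumed true rate of 10%, the PP NEC rate could be 11.0% to 13.7% on one reading (s of 10% to 30%) or 6.9% to 0% on the other (s = 25%, q of 50% to 100%). The text does not settle which.

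The values of p, s and q are assumptions. The harm is to the interpretation of a preliminary NEC result. It is not an inflated confirmatory error rate, since nothing confirmatory is tested, and the planned ITT analysis of NEC is untouched.

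**What to change.** **Preferred.** Delete the PP repeat sentence in SAP 8.3.3 and keep NEC and all other efficacy on ITT only, as 8.6 and the table list already have it. Bring the sentence on optional PP use into line. This costs only wording.

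**If a PP analysis is wanted:**
- Amend 8.6 to allow it as supportive, and name the analyses before unblinding.
- Remove both the NEC clause and the short-dosing deviation bullet; removing only one leaves selection in place.
- Apply one adherence rule to every infant: doses received against doses due up to the first of confirmed NEC, death, discharge, any protocol-mandated stop or suspension (including for feeding intolerance or sepsis), or the end of intended dosing. Stopping the count only at NEC, death or discharge would still drop infants stopped for other mandated reasons.

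This needs one derived variable from recorded dosing dates. Infants with very early events would qualify on few doses, which a listing can show. It also changes how the Table 2 minimum applies after early discharge, and the SAP should say so.

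**In either case,** reconcile the 70% and 75% footnotes with each other and with the tabled days, and correct the cross-reference to Protocol 11.2.3.

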8.3.4 Pharmacokinetics (PK) population

Not applicable in this study.

8.4 Demographic and Other Baseline Characteristics

All baseline summaries will be based on the ITT populations.

Maternal race, infant race, infant gender, whether the uses of resuscitation/stabilization support, supplement oxygen, PPV, CPAP, intubation, chest compression and epinephrine will be summarized using counts and percentages.

Maternal age, infant birth length (cm), BW (g), one- and five-minute Apgar score will be summarized with descriptive statistics (number of subjects [N], mean, standard deviation [SD], median, 25th, 75th quartiles, minimum [min], and maximum [max]).

Maternal Pregnancy History and Delivery of whether the mother consume/or use any alcohol, cigarette, or recreational drug will be summarized using counts and percentages.

The summary of Maternal History and Baseline Characteristics, Pregnancy History and Delivery, Infant History and Baseline Characteristics will be displayed by (i) dose group and BW stratum and (ii) by all BW strata combined for STP206 low dose, STP206 high dose and control group.

Maternal History and Baseline Characteristics, Pregnancy History and Delivery, Infant History and Baseline Characteristics will be presented in a listing.

8.5 Prior and Concomitant Therapy

Summary of prior and concomitant therapy will be based on safety population.

The World Health Organization (WHO) Drug Dictionary September 2013 will be used to classify prior and concomitant medications by preferred term and WHO Anatomical Therapeutic Chemical (ATC) classification of ingredients. Prior medications are defined as any medication

given prior to and stopped before the subject receives the first dose of study medication (Day 1). Concomitant medications are defined as any medication given to the subject starting on or after the day the subject received the first dose of study treatment (Day 1) or given prior to the subject receiving the first dose of study treatment (Day 1) and continuing to receive it during the study.

If the start date of medication is unknown and the end date is known, then the medication will be considered:

- Prior to study treatment if the end date is prior to the subject receiving the first dose of study treatment (Day 1)
- Concomitant to study treatment if the end date is either on or after the first dose of study treatment (Day 1) or the end date is unknown.

If both the start and end dates are unknown, then the medication will be considered to be “concomitant on-treatment”. For the purposes of determining the medication reference to the onset date for partial dates, missing months will be imputed to ‘01’, and missing days will be imputed to ‘01.’

Prior and concomitant medication will be summarized giving the number and percentage of subjects (n, (n/N*100)) by preferred name within each ATC, with ATC and preferred names sorted by descending frequency.

ATC classification level 3 will be used in summary tables and listings. If ATC classification level 3 is missing, then ATC classification level 2 will be used, however, if ATC classification level 2 is missing, then ATC classification level 1 will be used.

The summary of maternal medical history, infant prior and concomitant therapy will be displayed by (i) dose group and BW stratum and (ii) by all BW strata combined for STP206 low dose, STP206 high dose and control group.

8.6 Analysis of Efficacy Parameters

Descriptive summaries will consist of frequencies and percentages for categorical measures and of the number of subjects [N], mean, standard deviation [SD], median, 25th and 75th quartiles, minimum [min], and maximum [max] values for continuous measures. Descriptive summaries will be presented for each treatment group, BW strata, and all BW strata combined.

The incidence rates of the exploratory variables for those who received STP206 vs. control will be summarized and displayed.

The analyses of efficacy variables will be performed for ITT population only.

Efficacy will be displayed by (i) dose group and BW stratum and (ii) by all BW strata combined for STP206 low dose, STP206 high dose and control group.

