### 10.3.5. Adverse Event Assessment

AEs occurring in neonates will be determined based upon physical findings, functional findings, laboratory findings, and routine observation of the neonate. AEs will be assessed from the time of initial administration of blinded study treatment through 6 months following completion of dosing and be recorded regardless of severity or relationship to blinded study treatment. Ongoing AEs will be followed by standard NICU practice until resolution or stabilization. For each AE, the following information will be recorded:

- Onset date and time
- Resolution date and time
- Severity/intensity (see [Section 12.2.5](#))
- Relationship to study drug (see [Section 12.2.4](#))
- Serious or non-serious (see [Section 12.2.3](#))
- Actions taken to manage/treat the event
- Outcome of the event - resolved, resolved with sequelae, ongoing, death

Complications of prematurity (see [Section 10.5.2](#)) will be recorded separately and not recorded as AEs.

---

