## 10.5.2. Relevant Neonatal Morbidities/Complications of Prematurity

### 10.5.2.1. *Necrotizing Enterocolitis*

Necrotizing Enterocolitis, (see [Appendix B](#) for diagnostic and staging criteria) will be assessed through physical findings (abdominal distension & tenderness) and feeding tolerance. If NEC is suspected, an abdominal X-ray will be obtained to determine the presence of pneumatosis intestinalis, portal venous air, or free air.

If NEC is diagnosed, study drug administration will be discontinued immediately.

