### 10.5.2.5. *Other Complications of Prematurity*

Study staff will evaluate neonates for the following other clinical events:

- Spontaneous gastrointestinal perforation
- Patent ductus arteriosus requiring treatment with indomethacin, ibuprofen or surgery
- Late onset sepsis
- Late onset Candida sepsis

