### 12.3.1. Reporting Complications of Prematurity

Complications of prematurity will not be classified as AEs, but as study outcomes.

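### No planned Safety-population summary table shows NEC, perforation, IVH, treated PDA, ROP or BPD by treatment received

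*SAP*

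**What the plan says.** **Recording.** Protocol 10.3.5 says that complications of prematurity "will be recorded separately and not recorded as AEs". Protocol 12.3.1 repeats the rule: "Complications of prematurity will not be classified as AEs, but as study outcomes". The section headed "10.5.2. Relevant Neonatal Morbidities/Complications of Prematurity" covers NEC, ROP, BPD and IVH. Its last subsection, 10.5.2.5, adds "Spontaneous gastrointestinal perforation" and "Patent ductus arteriosus requiring treatment with indomethacin, ibuprofen or surgery".

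**Complications.** SAP 6.4.2 and 8.6.2.1 list these outcomes as secondary efficacy variables. SAP 8.6 then restricts the population: "The analyses of efficacy variables will be performed for ITT population only". SAP 8.3.2 defines ITT as everyone randomised, grouped by randomised arm. SAP 5.2 confirms that undosed infants are included.

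**Adverse events.** SAP 8.7 and 8.7.2 use the Safety population. SAP 8.3.1 says of it: "Subjects will be analyzed according to the treatment they actually received".

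**Per-protocol set.** SAP 8.3.3 also groups infants by treatment received. It says "This population may be used for analysis if subjects are dosed incorrectly", and it ends by promising a repeat of the primary and some secondary analyses in this set, without saying which.

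**The concern.** The primary objective is the safety and tolerability of a live bacterial product in preterm infants. Six complications that could represent harm are tabulated under one grouping rule, and AEs under another. If an infant receives the wrong treatment, that infant's AEs are counted in the column of the treatment given, and that infant's NEC or perforation in the column of the treatment assigned. A reader setting the AE tables beside the complication tables would then be comparing columns made up of different infants. With control cells of four, one such infant can reverse the direction of a displayed rate.

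As-randomised grouping is right for asking whether STP206 prevents NEC. It is not the natural display for asking whether infants exposed to STP206 came to harm. These outcomes serve both questions, and the plan provides a summary table for only the first.

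**Working it through.** The plan states no figure to reproduce, and the sample size was not derived statistically. The check is a reading of the two documents side by side, plus a small illustration.

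**1. Trace each type of event to its table (SAP section 11).**

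| Event | Recorded as | Summary tables | Population and grouping |
|---|---|---|---|
| NEC | study outcome | 14.2.2.1-3, 14.2.2.6-8 | ITT, as randomised |
| Perforation, IVH, treated PDA, ROP, BPD | study outcome | 14.2.4.1-3 | ITT, as randomised |
| AEs | AE | 14.3.1.x | Safety, as treated |
| SAEs, AEs leading to death | AE | 14.3.2.1.x, 14.3.2.3.x | Safety, as treated |

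No listed 14.3.x table is designed to show any of the six complications. Infant-level listings exist (16.2.6.1.1 and 16.2.6.5 to 16.2.6.9), but they are not summaries.

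**2. Check whether the per-protocol repeat closes the gap.** It does not, for four reasons.
- The secondary analyses to be repeated are not named.
- The only per-protocol tables listed are baseline characteristics (14.1.3.5-7 and 14.1.3.13-15).
- The set drops infants with a critical or major deviation, and infants below minimum dosing unless they have confirmed NEC. An infant with a perforation whose dosing stops early could drop out of it.
- The repeat contradicts the ITT-only sentence in SAP 8.6.

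**3. Check how the SAP treats other dual-role variables.** Growth classification and detection of STP206 organisms are secondary efficacy variables in SAP 6.4.2 and safety assessments in SAP 6.6. Both have Safety-population tables (14.3.6.2.x and 14.3.6.4.x). The six complications have none.

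**4. Illustrate the size.** Inputs: eight groups of 12 infants, randomised 2:1 (protocol 7.1).
- Per group: 12 × 2/3 = 8 STP206 and 12 − 8 = 4 control.
- Total: 8 × 12 = 96. Pooled over the four strata: 4 × 8 = 32 low dose, 4 × 8 = 32 high dose and 8 × 4 = 32 control.

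Assume that one infant randomised to control receives STP206 and develops NEC, and that there is no other event.

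| Display | STP206 | Control |
|---|---|---|
| One group, as randomised | 0/8 = 0% | 1/4 = 25% |
| One group, as treated | 1/9 = 11.1% | 0/3 = 0% |
| One pooled dose column, as randomised | 0/32 = 0% | 1/32 = 3.1% |
| One pooled dose column, as treated | 1/33 = 3.0% | 0/31 = 0% |

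The direction reverses in both. The pooled rows follow the SAP's own layout, which keeps low and high dose in separate columns.

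**5. Undosed infants.** A randomised infant who receives no dose is in ITT but not in the Safety population. One such control infant gives a denominator of 4 in the complication tables and 3 in the AE tables of that group.

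**6. Otherwise.** If every infant is dosed, and dosed as randomised, the two displays are identical.

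**The case against.** **The text on grouping is mixed.** SAP 8.3.3 promises an as-treated repeat of some secondary analyses and keeps confirmed NEC cases who miss minimum dosing. Protocol 13.2.3.1 describes the efficacy comparison in terms of treatment received, and SAP 8.6 does the same for the exploratory variables. SAP section 11 says further tables may be added. This stands in part: one cannot say that the documents fix these outcomes absolutely as randomised. But the text that points the other way conflicts with the ITT-only sentence and leads to no listed outcome table.

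**A reader might infer that the gravest harms never reach the safety tables.** The documents do not support that. Protocol 10.3.5.1 makes any sepsis an SAE, and 12.2.3 does the same for confirmed bacteremia. SAEs and AEs leading to death have Safety-population tables. Infection with a product organism is also a stopping event for DSMC review (protocol 7.1.1). Untreated PDA falls outside the listed complication, and protocol 10.5.2.4 grades IVH only from II to IV, so untreated PDA or grade I IVH might still be recorded as AEs. The gap is confined to the six complications as the protocol defines them.

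**The illustration needs two uncommon events in one infant.** This is fair. The documents give no misdosing rate. Assume 1% to 5% of controls are misdosed, and apply to all strata the roughly 10% NEC rate that protocol 5.1 cites for VLBW infants. The expected number among 32 controls is then 32 × 0.01 × 0.10 = 0.03 to 32 × 0.05 × 0.10 = 0.16. Protocol 10.8.1 also requires identity to be checked against the labelled syringes before dosing.

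**No data are lost.** In a study of about 100 infants, the listings of complications, randomisation (16.2.1.1) and exposure (16.2.5) would identify any misdosed infant. The DSMC sees secondary endpoints at every review. All comparisons are exploratory. This stands, and it limits the severity. It does not supply a summary table.

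**Conclusion.** The point holds, and it is minor. Six complications of prematurity are excluded from AE recording, and their only planned summary tables are in the as-randomised ITT set. No planned Safety-population summary shows them by treatment received, although safety is the primary objective and the SAP already gives other dual-role variables Safety tables.

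The numerical effect depends on an infant being misdosed, which SAP 8.3.3 foresees, or randomised and left undosed, which SAP 5.2 admits to ITT. Without either, nothing in the output changes. With one misdosed control infant who develops NEC, the direction of the displayed rates reverses, both within a group and in a pooled dose column. That is an illustration of sensitivity in small cells and not a forecast.

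**What to change.** Add to SAP 8.7 that Tables 14.2.2.1-3 (NEC) and 14.2.4.1-3 (other complications) are also produced in the Safety population by treatment actually received, as safety displays beside the AE tables. Keep the ITT versions as the efficacy displays, and qualify the ITT-only sentence in SAP 8.6 to match.

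Reconcile SAP 8.3.3 with 8.6: either name the secondary analyses to be repeated in the per-protocol set and list their tables, or remove the repeat. Align the received-treatment wording in SAP 8.6 with whichever grouping is meant, and record in SAP 5.2 any departure from protocol 13.2.3.1.

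The cost is a few sentences and about six reruns of existing table shells on a second population flag. No new data are needed.
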